## 9.5.2.3 Secondary Analysis for the Primary Aim

Although the parent study (on effectiveness of levofloxacin prophylaxis) will utilize standard principles of intent-to-treat analysis, those principles may be at odds with the goal of estimating the negative effects (resistance) of prophylaxis. Drop-out from the parent study might reduce power but be uninformative and unrelated to the eventual parent study outcome (incidence of bacteremia). In contrast, drop-out in this ancillary study might be acutely informative by being related to the emergence of an adverse event such as the development of infection due to resistant organism. Second, although randomization at baseline should balance all differences between the treatment groups by measured and unmeasured confounders, extra precautions are needed to guard against the potential bias of baseline covariates with chance imbalance from finite sample sizes. Additionally, there may be nonrandom assignment to additional antibiotics, and those post-randomization exposures might also bias results if they are not properly controlled. Finally, there is no guarantee that the subjects who enter the study will not carry resistant organisms at the time of initial enrollment. The presence of future carriage of resistant organisms by an individual is likely related to the presence of or absence of colonization at or prior to initiation of antimicrobial prophylaxis.

To address these issues, we propose a multivariate mixed-effects analysis that accounts for drop-out, variation in baseline covariates, and variation in post-randomization exposures (e.g. additional antimicrobials). A multivariate mixed-effects model has the versatility to be expanded to account for confounding from drop-out, covariate inequities from finite sample size, and administration of other antibiotics in addition to the prophylactic antimicrobials. For this model the multivariate outcome will be the 12 dichotomous outcomes (0 for no resistance and 1 for resistance) for each of the bacteria-antibiotic combinations. The model will account for the lack of independence of outcomes for each subject within a given measurement time, as well as the correlation of repeated measures over time. This multivariate mixed-effect model will attempt to assess the true causal effect of prophylactic levofloxacin on the risk of overall resistance among colonizing organisms.

## 9.5.2.4 Comparative Analyses for the Secondary Aim

Unlike the outcome for the primary aim which will be obtained at fixed timepoints, the outcomes for this secondary aim (positive sterile site culture with a resistant organism) will be present at varying times from study enrollment. Therefore, we propose a Cox proportional hazards regression model that will be adapted to address issues of concomitant nonrandomized treatment (time-dependent confounding), and informative drop-out. Each outcome (presence or absence of resistance for the specified group of infecting organisms and antibiotic) will be evaluated in separate models.

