#### **ABSTRACT**

Bacterial sepsis continues to be a leading cause of morbidity and toxic death in children receiving treatment for acute myeloid leukemia (AML), relapsed acute lymphoblastic leukemia (ALL) and for those undergoing hematopoietic stem cell transplant (HSCT). Data from adult studies suggest that antibiotic prophylaxis decreases the incidence of infection-related death in patients receiving intensive myelosuppressive therapy; however, antibiotic prophylaxis in pediatric patients is largely unstudied. This open-label, randomized, controlled trial will evaluate whether prophylactic therapy with levofloxacin will decrease the incidence of bacteremia in pediatric patients being treated with intensive chemotherapy for acute leukemia (AL) or for those undergoing HSCT. In addition, the study design will allow assessment of the potential risks of prophylactic therapy such as impact on host flora and quinolone-related musculoskeletal side effects. The ancillary study within this trial represents a unique opportunity to establish the relative risk for evolution of resistance and persistence of resistance among gastrointestinal colonizing organisms frequently associated with invasive bacterial infection. Such data are necessary to judge the balance between the risks and benefits of antibiotic prophylaxis and thus help determine whether prophylactic levofloxacin should be incorporated in clinical care of children and young adults who are at high risk of serious infections secondary to cancer therapy.

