#### 7.1.2.2 Sterile Site Cultures

Patients will have sterile site bacterial isolate data collected during the infection observation period. Sterile site cultures will be done as part of good patient care, for example blood cultures obtained in patients with new fevers. Decisions about what types of culture and when the cultures are drawn will be made according to local institutional practice.

Bacteria isolated from sterile site cultures will be processed at the microbiology labs at the local institutions caring for the patient. The final laboratory report for each bacterial isolate (including the bacteria name, date the culture was obtained, culture source, and antibacterial resistance profile) will be submitted via the document imaging system for central review. A panel of 4 committee members will centrally review all positive sterile site cultures and antibacterial resistance profiles. It is anticipated that the techniques for establishing an isolate's minimum inhibitory concentration (MIC) will vary between institutions. However, this variability should not have great impact on whether organisms are classified as resistant.

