## 9.3 Statistical Analysis Methods

## 9.3.1 Endpoints

## 9.3.1.1 Primary Endpoint

The primary endpoint is occurrence of at least 1 episode of true bacteremia during the study timeframe of 2 cycles of chemotherapy or 1 transplant procedure among AL and HSCT subjects respectively. Similar to others, 49,50 positive cultures with common contaminants, namely coagulase negative *Staphylococcus*, *Corynebacterium* species, *Propionibacterium acnes*, *Bacillus* species, *Micrococcus* species, *Clostridium* species (except *C. septicum* and *C. perfringens*) and *Neisseria* species (except *N. gonorrhea* and *N. meningitides*), will require 2 positive blood cultures for the same organism within the same episode (irrespective of timing between the 2 or more cultures) or be associated with sepsis syndrome to be considered true bacteremia. We will use international consensus definitions for defining sepsis. 58-61 The observation period for infectious outcomes, including the primary endpoint will be the same for both arms irrespective of whether the child discontinues levofloxacin early for those allocated to that arm.

Specifically, the infection observation period will begin Day 3 of each cycle of chemotherapy and will end when the ANC is  $> 200/\mu L$  and rising post nadir, or at Day 60 if an ANC of  $> 200/\mu L$  has not been reached or Day 1 of the next cycle of chemotherapy, whichever occurs first. For patients undergoing HSCT, the observation period will begin on Day -2 from stem cell infusion and end when the ANC is  $> 200/\mu L$  and rising post nadir, or at Day 60 if an ANC  $> 200/\mu L$  has not been reached or the first day of subsequent cancer therapy, whichever occurs first.

Patients will be considered evaluable for the primary endpoint if data on bacteremia during the infection observation period are available, regardless of protocol treatment compliance.

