#### 9.3.1.2 Secondary Endpoints

Stool surveillance testing will investigate for the following resistance patterns among stool commensals at the start and end day of each treatment period: the susceptibility of *E. coli, K. pneumoniae*, and *P. aeruginosa* stool or peri-rectal swab isolates to cefepime, imipenem and levofloxacin; the susceptibility of *S. mitis* peri-rectal swab isolates to cefepime, levofloxacin and penicillin. Additionally, the presence of carbapenem-resistant Enterobacteriaceae will be screened from each enrolled patient's second collected stool or peri-rectal swab. The trajectory of the resistance patterns for the gastrointestinal isolates colonizing each patient will then be evaluated. Data regarding the resistance patterns of bacterial isolates from all sterile site cultures will be described. In interpreting antimicrobial sensitivity testing of both gastrointestinal organisms and organisms isolated from sterile sites, an intermediate result will be considered resistant for analytic purposes.

A secondary endpoint will be the duration of parenteral antibiotic administration during the study timeframe of 2 cycles of chemotherapy or 1 transplant procedure. Each day of parenteral administration will be collected irrespective of the indication or type of antibiotic given and the observation timeframe will be the same as that described for the primary endpoint. Other secondary endpoints include the incidence of febrile neutropenia, severe infection and death from bacterial infection. Severe bloodstream bacterial, fungal, and clinically documented infections and death from bacterial infection will consist of episodes of infection that are graded as CTCAE version 4 Grades 4 or 5 respectively. Secondary

endpoints on musculoskeletal adverse events and particularly tendinopathy (tendonitis and tendon rupture) will be collected. CDAD will be defined as a positive *C. difficile* toxin assay result and diarrhea, CTCAE version 4, Grade 2 and higher. Microbiologically-proven IFIs will be recorded.

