## 9.5.1.2 Secondary Aim

The secondary aim is to determine whether prophylactic levofloxacin versus no levofloxacin is associated with an increased risk for the development of bacteremia or sterile site infection from either Gram positive or Gram negative resistant organisms. The following resistance scenarios will be considered independently:

- 1a. Levofloxacin resistant Gram positive and Gram negative organisms
- 1b. Cefepime resistant Gram positive and Gram negative organisms
- 1c. Imipenem resistant Gram positive and Gram negative organisms
- 1d. Penicillin resistance for *S mitis* only

The secondary hypotheses for these secondary aims are that the use of levofloxacin prophylaxis is associated with an increased risk of infection with levofloxacin resistant Gram positive as well as Gram negative organisms. Additionally, exposure to levofloxacin prophylaxis results in an increased risk of infection with both Gram positive and Gram negative organisms resistant to cefepime and imipenem. Lastly, levofloxacin prophylaxis is associated with an increased risk of penicillin resistant *S mitis*.

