Only those patients with AL will have a stool or peri-rectal specimen obtained after a second course of levofloxacin prophylaxis or standard of care. It is estimated that 40% of the study enrollees will have AL (133 per arm). Again assuming that 80% consent to this ancillary study this will result in approximately 106 AL patients in each study arm contributing a stool or peri-rectal swab after a second course of prophylaxis or after standard of care. Maintaining all other parameters noted above, this scenario would still yield a power of 0.86 to detect a difference of 1.25 in the mean resistance counts between the two study arms. Power calculations were done using Stata v11.1 (Stata Corp, College Station TX, 2009).

For the secondary aims of this sub-study, we anticipate that all positive sterile site cultures from all evaluable neutropenic episodes in the parent trial will be available for analysis. Based on the frequency of Gram negative bacteremia events per neutropenic episodes that were resistant to levofloxacin in the adult levofloxacin prophylaxis trial (1% of neutropenic episodes on placebo versus 3% of neutropenic episodes on levofloxacin), it is anticipated that our study size will be insufficiently powered to analyze this outcome as a primary event. Assuming n=466 neutropenic episodes per treatment arm (333 patients per treatment arm with 40% having AL and 2 neutropenic periods and 60% undergoing HSCT with 1 neutropenic episode) and assuming the above noted event rate for each arm (1% versus 3%), there would be 0.49 power to detect a statistically significant difference. Even if the event rate for resistance is as high as 8.7% (as was seen for Gram positive organisms in the adult trial), the power for this study would only exceed 0.80 if the event rate of resistance in the treatment arm was almost doubled to 15%. Power calculations were done using PASS 2008 (NCSS, Kaysville, UT, 2008).

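### The resistant-infection outcome in 9.5.2.4 is worded as a positive culture and does not carry over the contaminant rule of 9.3.1.1, so single resistant contaminants can count as events

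*Combined protocol and SAP*

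**What the plan says.** Four places in the combined protocol and SAP bear on this outcome.

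- **The aim (9.5.1.2)** concerns an "increased risk for the development of bacteremia or sterile site infection from either Gram positive or Gram negative resistant organisms".
- **The analysis (9.5.2.4)** fits separate Cox models and explains the choice by saying that "the outcomes for this secondary aim (positive sterile site culture with a resistant organism) will be present at varying times from study enrollment". Later in the same paragraph it refers to infecting organisms.
- **The primary endpoint (9.3.1.1)** lists common contaminants, such as coagulase-negative Staphylococcus, Corynebacterium, Bacillus and Micrococcus species. Such a culture "will require 2 positive blood cultures for the same organism within the same episode", or an association with sepsis syndrome, before it counts as true bacteremia. The rule is not repeated or cited in 7.1.2.2, 9.3.1.2 or 9.5.
- **The handling of cultures (7.1.2.2)** leaves sampling to the sites: "Decisions about what types of culture and when the cultures are drawn will be made according to local institutional practice". It adds: "A panel of 4 committee members will centrally review all positive sterile site cultures and antibacterial resistance profiles". It gives the panel no contaminant criterion for the resistance outcome and does not say that the panel is blinded to arm.

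Under 9.3.1.2, "an intermediate result will be considered resistant for analytic purposes", which widens the set of isolates that qualify.

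**The concern.** The aim is about infection; the event is worded as a culture result. Take a child with one coagulase-negative Staphylococcus blood culture, no second positive culture and no sepsis. In the primary analysis this child has no bacteremia. If the isolate is intermediate or resistant to levofloxacin, cefepime or imipenem, the wording of 9.5.2.4 makes the same child an event in the matching Gram positive model.

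Section 9.5.2.2 presents resistance among infecting organisms as an important safety question. Contaminant events carry no information on infection. How many arise depends on how many cultures are drawn, and in an open-label trial with local sampling practice that number need not be the same in both arms. What is at stake is whether the Cox models estimate the effect on resistant infection or a mixture of that effect and culture contamination.

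**Working it through.** **Which models are touched.** In the 9.3.1.1 list only Neisseria is Gram negative, so nearly all the misclassification falls on the Gram positive models. *S. mitis* is not listed, so the penicillin-resistant *S. mitis* model is unaffected.

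**Inputs from 9.5.3.** There are 333 patients per arm, 40% with AL (two neutropenic periods) and 60% with HSCT (one): 333 × (0.4 × 2 + 0.6 × 1) = 466.2, matching the plan's 466 episodes per arm. Event rates are 1% versus 3% (Gram negative) and 8.7% versus 15% (Gram positive). Section 9.5.3.2 states no alpha; I assume two-sided 0.05, as in 9.3.2.

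**Formula.** With d = p2 − p1 and p̄ the mean of the two rates:

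- se0 = √(2p̄(1 − p̄)/n)
- se = √(p1(1 − p1)/n + p2(1 − p2)/n)
- continuity-corrected power = Φ[(d − 1/n − 1.96·se0)/se]

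**Reproducing the plan.**

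- 1% versus 3%: (0.0200 − 0.0021 − 0.0180)/0.0091 is about −0.01, so power is 0.495. The plan states 0.49. Without the correction the result is 0.59, so the corrected form is the one to use.
- 8.7% versus 15%: (0.0630 − 0.0021 − 0.0415)/0.0211 = 0.92, so power is 0.82. This agrees with the plan's statement that 0.80 is exceeded at about 15%. Uncorrected power is 0.85.

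**Adding contaminants.** Let c be the chance per episode of a resistant single-contaminant culture, independent of true infection. The observed rate is 1 − (1 − p)(1 − c). For example, at c = 3% the control rate is 1 − 0.913 × 0.97 = 11.4%. Every value of c is an assumption.

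| c, control vs levofloxacin | Observed rates | Ratio | Excess (points) | Corrected power |
|---|---|---|---|---|
| none | 8.7% vs 15.0% | 1.72 | 6.3 | 0.82 |
| 1% vs 1% | 9.6% vs 15.9% | 1.65 | 6.2 | 0.79 |
| 2% vs 2% | 10.5% vs 16.7% | 1.59 | 6.2 | 0.76 |
| 3% vs 3% | 11.4% vs 17.6% | 1.53 | 6.1 | 0.73 |
| 5% vs 3% | 13.3% vs 17.6% | 1.32 | 4.3 | 0.41 |
| 3% vs 4% | 11.4% vs 18.4% | 1.61 | 7.0 | 0.83 |

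With equal c the ratio shrinks and power falls. With unequal c the excess can shrink (5% versus 3%) or grow (3% versus 4%).

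**No true effect.** With 8.7% in both arms and c of 5% versus 10%, the observed rates are 13.3% and 17.8%. The chance of a significant result is then about 0.45 (0.49 uncorrected).

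**Gram negative.** For 1% versus 3%, a c of 0.2% in both arms moves corrected power from 0.495 to 0.46.

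These figures use a two-proportion test on episodes, in line with the plan's own calculation. The planned Cox models would show the same kind of attenuation.

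**The case against.** The strongest reply is that infection is the natural reading. Section 9.5.1.2 says so, 9.5.2.1, 9.5.2.2 and 9.5.2.4 all refer to infecting organisms, 9.3.1.1 is the only definition of bacteremia in the document, and a panel sees every positive culture. This stands in part: the text is inconsistent rather than unequivocal, and the panel might exclude contaminants in practice. But no rule tells it to, and the one phrase that describes the event is the culture phrase.

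Section 9.5.3.2 says that "we anticipate that all positive sterile site cultures from all evaluable neutropenic episodes in the parent trial will be available for analysis". A reader might take this as confirming that every culture is an event. It speaks only of which data will be at hand, and I do not rely on it.

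A reader might also infer that contaminants will hide a harm: cultures follow fever, levofloxacin is hypothesised to reduce fever with neutropenia, so controls would collect more contaminants. The documents do not establish this. They give no culture counts, no contaminant rates and no resistant share by arm. If levofloxacin selects resistant skin flora, contaminants could instead create an apparent harm.

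Two further points stand. The 8.7% comes from an adult trial whose culture definition is not given here, so it may already include contaminants. And 9.5.3.2 already concedes that this outcome is underpowered and makes colonization the primary endpoint of the ancillary study, which limits the consequence.

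**Conclusion.** The point holds as a mismatch between the aim and the stated event. Followed literally, 9.5.2.4 counts single resistant or intermediate contaminant blood cultures that the primary analysis rejects. The effect is confined almost wholly to the Gram positive models. It dilutes the contrast if contaminants are equal between arms and biases it in an unknown direction if they are not; the stronger claim that it masks harm is not supported.

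The size is illustrative. A drop in power from 0.82 to between 0.79 and 0.73 rests on assumed equal rates of 1% to 3%, on independence from true infection, and on 8.7% and 15% being rates of true infection. The case for a change does not depend on those figures: the rule already exists, and either direction of bias argues for applying it.

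**What to change.** 1. State in 9.5.1.2 and 9.5.2.4 that a blood culture event must be true bacteremia under 9.3.1.1, contaminant rule included, with an isolate resistant to the antibiotic in question.
2. State in advance a criterion for calling a non-blood sterile site isolate an infection.
3. Have the existing four-member panel classify all positive cultures against these criteria without knowledge of arm.
4. Keep the any-positive-culture outcome as a sensitivity analysis, and keep the listing of all isolates as the description for objective 1.2.1(a).

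The cost is a few sentences of text and removal of arm from what the panel sees. The primary endpoint already needs the contaminant decision for blood cultures. The non-blood criterion should be checked against what the panel receives: 7.1.2.2 lists organism, date, source and resistance profile, so a criterion that uses clinical findings may need a little more information. The statistical price is slightly fewer events in the Gram positive models.

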## 9.5.2.5 Descriptive Analysis for the Tertiary Aim

This final aim focuses on describing the frequency of stool colonization with any carbapenem-resistant Enterobacteriaceae in patients after receiving or not receiving levofloxacin prophylaxis. The frequency of colonization with these resistant bacteria among children with leukemia is currently unknown. While it is likely that the frequency of carbapenem-resistant commensals will be too small to allow for formal statistical comparison between the two study treatment arms, the collected stool or peri-rectal specimens represent an ideal opportunity to define the epidemiology of these highly resistance organisms in this patient population after differing antibiotic exposures.

# 9.5.3 Estimated Sample Size and Event Rates

## 9.5.3.1 Available Sample size

A total of 666 eligible and evaluable study subjects will be enrolled in the parent study, 333 per treatment arm over the study period. Since this ancillary study does not include additional study visits and consists of obtaining stool or peri-rectal swabs for bacterial culture, a relatively easy and non-invasive procedure, we anticipate that at least 80% of subjects in the parent trial will also participate in this ancillary resistance study resulting in an effective sample size of 532 patients (266 in each study arm) for the primary aim of this ancillary study. For the secondary aim of this study the data for sterile site cultures are expected to be available for all 666 parent trial enrollees (333 in each study arm).

## 9.5.3.2 Event Rates for Power Calculations

Contemporary data are limited on the frequency at which colonizing organisms can be isolated from stool or peri-rectal swabs for each of the organisms of interest. It has been shown in a small study of adult patients with AL, that 31% of patients had *P. aeruginosa* identified on at least 1 stool specimen. However, the goal of this ancillary study is to determine whether the presence of organisms retaining resistance to certain antibiotics are increased above baseline in patients receiving levofloxacin prophylaxis compared to those not receiving prophylaxis. Thus for each swab result, a dichotomous interpretation of each bacteria-antibiotic combination (presence versus absence of the resistant organism) is most appropriate. Interpreting swab results in this way will make the results of all swab specimens informative in the final analysis.

The evolution of resistance for each organism-antibiotic combination of interest is not known, and thus the anticipated mean change in resistance counts from baseline to post-exposure cannot be reasonably estimated for either treatment arm. Instead, we evaluated the power to detect various differences in the mean change of resistance counts between the 2 study groups. Assuming that each study arm will yield 266 (assuming 80% of parent trial patients enroll in this ancillary study) evaluable specimens at baseline and post prophylaxis or standard of care timepoints, then this study will have 97% power to detect a difference between the two study group mean resistance counts as small as 1.0. This power calculation also assumes a substantial standard deviation in the mean of the difference in resistance counts of 3.0. Thus, there is power to detect even a small change in the mean difference of resistance between the two study arms.

Only those patients with AL will have a stool or peri-rectal specimen obtained after a second course of levofloxacin prophylaxis or standard of care. It is estimated that 40% of the study enrollees will have AL (133 per arm). Again assuming that 80% consent to this ancillary study this will result in approximately 106 AL patients in each study arm contributing a stool or peri-rectal swab after a second course of prophylaxis or after standard of care. Maintaining all other parameters noted above, this scenario would still yield a power of 0.86 to detect a difference of 1.25 in the mean resistance counts between the two study arms. Power calculations were done using Stata v11.1 (Stata Corp, College Station TX, 2009).

For the secondary aims of this sub-study, we anticipate that all positive sterile site cultures from all evaluable neutropenic episodes in the parent trial will be available for analysis. Based on the frequency of Gram negative bacteremia events per neutropenic episodes that were resistant to levofloxacin in the adult levofloxacin prophylaxis trial (1% of neutropenic episodes on placebo versus 3% of neutropenic episodes on levofloxacin), it is anticipated that our study size will be insufficiently powered to analyze this outcome as a primary event. Assuming n=466 neutropenic episodes per treatment arm (333 patients per treatment arm with 40% having AL and 2 neutropenic periods and 60% undergoing HSCT with 1 neutropenic episode) and assuming the above noted event rate for each arm (1% versus 3%), there would be 0.49 power to detect a statistically significant difference. Even if the event rate for resistance is as high as 8.7% (as was seen for Gram positive organisms in the adult trial), the power for this study would only exceed 0.80 if the event rate of resistance in the treatment arm was almost doubled to 15%. Power calculations were done using PASS 2008 (NCSS, Kaysville, UT, 2008).

Although the anticipated increase (2 percentage points) in sterile site cultures positive for resistant bacteria may be considered modest, such an increase may be clinically relevant if levofloxacin prophylaxis ultimately becomes standard of care for larger numbers of patients. Because this secondary aim is limited by the likely low event rate, evaluation of differences in resistance among colonizing organisms must be used as the primary endpoint. Based on the background discussion above, when patients are infected it is often the result of organisms to which they are colonized. Therefore, it is reasonable to suggest that if there is a significant increase in the resistance among colonizing organisms, then this could translate into a clinically important increase in infections from resistant organisms with worse clinical outcomes. 66,67

